8.4 Informed consent

The Principal Investigator will:

- Ensure each subject is given full and adequate oral and written information about the nature, purpose, possible risk, and benefit of the study
- Ensure each subject is notified that they are free to discontinue from the study at any time

- Ensure that each subject is given the opportunity to ask questions and allowed time to consider the information provided
- Ensure each subject provides signed and dated informed consent before conducting any procedure specifically for the study
- Ensure the original, signed Informed Consent Form(s) is/are stored in the Investigator's Study File
- Ensure a copy of the signed Informed Consent Form is given to the subject
- Ensure that any incentives for subjects who participate in the study as well as any provisions for subjects harmed as a consequence of study participation are described in the Informed Consent Form that is approved by an EC

A separate Informed Consent Form will be provided for genotyping.

8.5 Changes to the protocol and informed consent form

Study procedures will not be changed without the mutual agreement of the Principal Investigator and AstraZeneca.

If there are any substantial changes to the Clinical Study Protocol, then these changes will be documented in a Clinical Study Protocol Amendment and where required in a new version of the Clinical Study Protocol (Revised Clinical Study Protocol).

The Amendment is to be approved by the relevant EC and if applicable, also the national regulatory authority approval, before implementation. Local requirements are to be followed for Revised Clinical Study Protocols.

AstraZeneca will distribute any subsequent Amendments and new versions of the Clinical Study Protocol to each Principal Investigator. For distribution to EC see Section 8.3.

If an Amendment requires a change to a study centre's Informed Consent Form, AstraZeneca and the study centre's EC are to approve the revised Informed Consent Form before the revised form is used.

If local regulations require, any administrative change will be communicated to or approved by each EC.

8.6 Audits and inspections

Authorised representatives of AstraZeneca, a regulatory authority, or an EC may perform audits or inspections at the study centre, including source data verification. The purpose of an audit or inspection is to systematically and independently examine all study-related activities and documents, to determine whether these activities were conducted, and data were recorded, analysed, and accurately reported according to the Clinical Study Protocol, Good Clinical

Practice, guidelines of the International Conference on Harmonisation, and any applicable regulatory requirements. The Investigator will contact AstraZeneca immediately if contacted by a regulatory agency about an inspection at the centre.

9. STUDY MANAGEMENT

9.1 **Pre-study activities**

Before the first subject is entered into the study, it is necessary for a representative of AstraZeneca to visit the study centre to:

- Determine the adequacy of the facilities
- Determine availability of appropriate subjects for the study
- Discuss with the Investigator(s) (and other staff involved with the study) their responsibilities with regard to Clinical Study Protocol adherence, and the responsibilities of AstraZeneca or its representatives. This will be documented in a Clinical Study Agreement between AstraZeneca and the Investigator

9.2 Training of study site personnel

Before the first subject is entered into the study, an AstraZeneca representative will review and discuss the requirements of the Clinical Study Protocol and related documents with the investigational staff and also train them in any study specific procedures and system(s) utilised.

The Principal Investigator will ensure that appropriate training relevant to the study is given to all of these staff, and that any new information relevant to the performance of this study is forwarded to the staff involved.

The Principal Investigator will maintain a record of all individuals involved in the study (medical, nursing, and other staff).

9.3 Monitoring of the study

During the study, an AstraZeneca representative will have regular contacts with the study centre, including visits to:

- Provide information and support to the Investigator(s)
- Confirm that facilities remain acceptable
- Confirm that the investigational team is adhering to the Clinical Study Protocol, that data are being accurately and timely recorded in the CRFs, that biological samples are handled in accordance with the Laboratory Manual and that investigational product accountability checks are being performed

- Perform source data verification (a comparison of the data in the CRFs with the subject's medical records at the hospital or practice, and other records relevant to the study) including verification of informed consent of participating subjects. This will require direct access to all original records for each subject (eg, clinic charts)
- Ensure withdrawal of informed consent to the use of the subject's biological samples is reported and biological samples are identified and disposed of/destroyed accordingly, and the action is documented, and reported to the subject

The AstraZeneca representative will be available between visits if the Investigator(s) or other staff at the study centre needs information and advice about the study conduct.

9.3.1 Source data

Refer to the Clinical Study Agreement for location of source data.

9.4 Study agreements

The Principal Investigator at the study centre should comply with all the terms, conditions, and obligations of the Clinical Study Agreement, or equivalent, for this study. In the event of any inconsistency between this Clinical Study Protocol and the Clinical Study Agreement, the terms of Clinical Study Protocol shall prevail with respect to the conduct of the study and the treatment of subjects and in all other respects, not relating to study conduct or treatment of subjects, the terms of the Clinical Study Agreement shall prevail.

Agreements between AstraZeneca and the Principal Investigator should be in place before any study-related procedures can take place, or subjects are enrolled.

9.4.1 Archiving of study documents

The Investigator will follow the principles outlined in the Clinical Study Agreement.

9.5 Study timetable and end of study

The end of the study is defined as "the last visit of the last subject undergoing the study".

The study is expected to start in and to end by

The study may be terminated at the study centre if the study procedures are not being performed according to Good Clinical Practice, or if recruitment is slow. AstraZeneca may also terminate the entire study prematurely if concerns for safety arise within this study or in any other study with AZD8931.

10. DATA MANAGEMENT

Data management will be performed by

A 21 Code of Federal Regulations part 11 compliant EDC system will be used for this study. Electronic CRFs will be produced by for each subject. The majority of study data collected will be either directly entered by clinical research staff or directly captured from devices onto the electronic CRF. Data will be available for AstraZeneca review via pre-defined reports extracted from the database at agreed intervals. The electronic CRFs must be kept in order and up-to-date so that they reflect the latest observations on the enrolled subjects.

When direct data entry onto the electronic CRF is inappropriate or impractical, data will be collected on paper source documents and subsequently transcribed, where necessary, onto the electronic CRFs by the clinical research staff of All source documents will be retained by Photocopies of completed source documents will be provided only if essential (ie, for regulatory purposes) at the request of the AstraZeneca.

Laboratory data are managed within the LIMS and only the date and time of sampling are recorded in the electronic CRF. Data that is not directly captured, eg, safety laboratory results and AE coding, are managed externally from the main study database. These data will be merged with the data from the main study database in post-production. Datasets supplied to the sponsor will contain all study data.

The informed consent will be kept with a copy of the completed source documents in the appropriate file folder provided, or a note to indicate where the records can be located. All records should be kept in conformance to applicable national laws and regulations.

All electronic CRF entries, corrections, and alterations must be made by the Investigator or other, authorised, study centre staff and only by individuals who have received training on the EDC system. Study centre staff may be allowed access to the system only after training is completed. Training must be documented and a log of all EDC users and their rights within the system be maintained.

The Data Management Plan will describe the methods used to collect, check and process clinical data in detail. It will also clarify the roles and responsibilities for the different functions and staff involved in the data management process.

Validity and consistency of data will be checked by employing pre-programmed data validation rules that will be applied to the data extracted from the EDC system during the course of the study. The data management team will raise queries in the EDC system to resolve discrepancies. The Investigator must verify that all data entries in the electronic CRFs are accurate and correct. After completion of the study and when all collected data is validated, the database will be locked. Final data will be extracted from the EDC system and delivered to AstraZeneca in the form of SAS[®] datasets in accordance with defined

AstraZeneca project standards. A PDF copy of the electronic CRF will be produced for each subject and included in the final delivery.

The EDC system will keep track of all data entry, alterations and query resolution in an audit trail. The audit trail will form an integral part of the database and will be archived alongside with the Dictionary coding. Medical coding is done using the most current version of Medical Dictionary for Regulatory Activities (MedDRA) and AstraZeneca Drug Dictionary.

Management of external data

Data management determines the format of the data to be received from external vendors and coordinates the flow of data to an external environment or clinical database. External data reconciliation will be done with the clinical database as applicable.

SAE/AE Reconciliation

Serious Adverse Event Reconciliation Reports are produced and reconciled with the Patient Safety database and/or the study centre.

Data verification and validation

The study data verification will be carried out by a site monitor comparing database entered data to source documents (ie, ECG printouts, laboratory results and other health records at the study centre). Questions and corrections will be noted and verified by the Investigator.

Pharmacogenetics

Any genotype data generated in this study will be stored in the AstraZeneca genotyping LIMS database, or other appropriate secure system within AstraZeneca and/or third party contracted to work with AstraZeneca to analyse samples. The results from this genetic research may be reported in the Clinical Study Report for the main study, or in a separate report as appropriate.

11. EVALUATION AND CALCULATION OF VARIABLES

11.1 Calculation or derivation of safety variable(s)

All AEs will be collected for each subject from the time when informed consent is obtained (Visit 1) until the follow-up visit. Adverse events that occur before dosing will be reported separately.

Change-from-baseline variables will be calculated for the safety variables listed below, as the post-treatment value minus the value at baseline. The baseline values will be as follows:

• Clinical laboratory tests: Day -1

- Vital signs (including supine and standing blood pressure): Day 1 predose
- ECG: Day 1 predose

11.1.1 Other significant adverse events (OAE)

During the evaluation of the AE data, an AstraZeneca medically qualified expert will review the list of AEs that were not reported as SAEs and discontinuations due to AEs. Based on the expert's judgement, significant AEs of particular clinical importance may, after consultation with the Global Patient Safety Physician, be considered other significant adverse events (OAEs) and reported as such in the Clinical Study Report. A similar review of laboratory/vital signs/ECG data will be performed for identification of OAEs.

Examples of these are marked haematological and other laboratory abnormalities, and certain events that lead to intervention (other than those already classified as serious), dose reduction or significant additional treatment.

11.2 Calculation or derivation of pharmacokinetic variables

The PK analyses of the plasma concentration data for AZD8931 and o-desmethyl AZD8931, as well as the radioactivity data for whole blood, plasma, urine, and faeces, will be performed at . Pharmacokinetic analyses will be conducted according to Standard Operating Procedures and Work Instructions for PK analyses if not otherwise specified.

Pharmacokinetic parameters will be derived using noncompartmental method with WinNonlin Professional Version 5.2 or higher (Pharsight Corp., Mountain View, California, United States of America) or SAS[®] Version 9.1 or higher (SAS Institute, Inc., Cary, North Carolina, United States of America). The actual sampling times will be used in the PK parameter calculations. Nominal times will be used for any interim PK analyses.

The following PK parameters will be derived from AZD8931 and o-desmethyl AZD8931 (if feasible) whole blood and plasma concentration data:

- Area under the concentration-time curve from zero to infinity (AUC)
- Area under the concentration-time curve from zero to the time of the last quantifiable concentration or radioactivity $(AUC_{(0-t)})$
- Area under the concentration-time curve from zero to 12 hours $(AUC_{(0-12)})$
- Area under the concentration-time curve from zero to 24 hours $(AUC_{(0-24)})$
- Maximum concentration (C_{max})
- Time to maximum concentration (t_{max})

- Terminal half-life $(t_{\frac{1}{2}\lambda z})$
- Apparent plasma clearance (CL/F), for AZD8931 only
- Apparent volume of distribution during terminal phase (V_z/F) , for AZD8931 only
- Volume of distribution at steady state (V_{ss}/F), for AZD8931 only
- Metabolite to parent ratio of AUC (MR_{AUC}) for AZD8931 and o-desmethyl AZD8931 only
- Metabolite to parent ratio of C_{max} (MR_{Cmax}) for AZD8931 and o-desmethyl AZD8931 only

The following PK parameters will be calculated for diagnostic purposes and listed, but will not be summarised:

- Terminal elimination rate constant (λ_z). Lambda z and related parameters will be reported only if coefficient of determination (Rsq) is greater than or equal to 0.80
- The time interval (h) of the log-linear regression used to determine $t_{\frac{1}{2}\lambda z}$
- Number of data points included in the log-linear regression analysis
- Rsq for calculation of λ_z
- Percentage of AUC obtained by extrapolation (%AUCex). If the %AUCex is greater than 30%, then AUC will not be reported

Any anomalous concentration values observed at the predose time point shall be identified in the PK analysis review documentation with a description of how the value was treated for the computation.

If an anomalous concentration value is observed at the terminal phase and is judged as physiologically unreasonable, it will be excluded from computing PK parameter estimates.

The following PK parameters will be calculated from AZD8931 and o-desmethyl AZD8931 (if feasible) whole blood, plasma, urine, and faeces radioactivity data:

- Area under the whole blood and plasma radioactivity-time curve (AUC)
- Amount of radioactivity excreted in urine (Ae_u)
- Amount of radioactivity excreted in faeces (Ae_f)
- Amount of radioactivity excreted in urine and faeces (Ae_{u+f})

- Radioactivity excreted in urine as a percentage of dose (fe_u)
- Radioactivity excreted in faeces as a percentage of dose (fe_f)
- Radioactivity excreted in urine and faeces as a percentage of dose (fe_{u+f})

The ratio of plasma AZD8931 AUC versus plasma radioactivity AUC, the ratio of plasma o-desmethyl AZD8931 AUC versus plasma radioactivity AUC, and the ratio of whole blood radioactivity AUC versus plasma radioactivity AUC will be calculated for each subject.

Additional PK parameters will be determined if deemed appropriate.

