Healthy male subjects, aged 50 to 65 years (inclusive) with regular daily bowel movements

Investigational product, dosage and mode of administration

Each subject will receive a single oral dose of 160 mg [¹⁴C]-labelled AZD8931, containing 7.4 MBq (200 μ Ci) administered as an oral solution.

Comparator, dosage and mode of administration

None

Duration of treatment

A single dose of AZD8931 will be administered. The study will consist of 3 visits. Visit 1, Screening will take place within 28 days before Visit 2, Day 1. Visit 2 will be the residential period when each subject will be resident in the study centre for 11 days from Day -1 until Day 11 (240 hours postdose). Visit 3, Follow-up will occur 5 to 10 days after the last sample has been collected.

Outcome variable(s):

• Pharmacokinetics

AZD8931 and o-desmethyl AZD8931 (AZD8931 metabolite) whole blood and plasma concentrations will be used to assess the following parameters, as applicable:

Area under the plasma concentration-time curve from zero to infinity (AUC); area under the plasma concentration-time curve from zero to the time of the last quantifiable radioactivity or concentration (AUC_(0-t)); area under the plasma concentration-time curve from zero to 12 hours (AUC₍₀₋₁₂₎); area under the plasma concentration-time curve from zero to 24 hours (AUC₍₀₋₂₄₎); maximum plasma concentration (C_{max}); time to maximum plasma concentration (t_{max}); terminal half-life (t_{½λz}); apparent plasma clearance (CL/F); apparent volume of distribution during terminal phase (V_z/F); volume of distribution at steady state (V_{ss}/F); metabolite to parent ratio of AUC (MR_{AUC}); and metabolite to parent ratio of C_{max} (MR_{Cmax}).

Whole blood, plasma, urine, and faeces radioactivity data will be used to assess the following parameters, as applicable:

AUC from whole blood and plasma radioactivity-time curvel; amount of radioactivity excreted in urine (Ae_u); amount of radioactivity excreted in faeces (Ae_f); amount of radioactivity excreted in urine and faeces (Ae_{u+f}); radioactivity excreted in faeces as a percentage of dose (fe_u); radioactivity excreted in faeces as a percentage of dose (fe_f); and radioactivity excreted in urine and faeces as a percentage of dose (fe_{u+f}).

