3.1 Overall study design and flow chart

This is an open label, single dose study conducted at a single study centre in 6 healthy male subjects. All subjects will receive a single dose of $[^{14}C]$ AZD8931 on Day 1.

The study will consist of 3 visits. Visit 1, Screening will take place within 28 days before Visit 2, Day 1. Visit 2 will be the residential period when each subject will be resident in the study centre for 11 days from Day -1 until Day 11 (240 hours postdose). Visit 3, Follow-up will occur 5 to 10 days after the last sample has been collected.

The study flow chart is presented in Figure 1 and the study assessments in Table 1.

Figure 1 Study flow chart

[figure not shown]

Table 1Study assessments

Visit	Visit 1 (screening)		sit 2 ial period)	Visit 3 (Follow-up)
Day	≤28 days before Visit 2	Day -1	Days 1-11	5-10 days after last sample collection
Inclusion/exclusion criteria	Х			
Informed consent	Х			
Demographic data	Х			
Medical history	Х			
Drugs of abuse and alcohol urine screen	X°	Х		
Serology for hepatitis and HIV	Х			
Height and weight measurements	Х			X^n
Admission to study centre		Х		
Dosing			\mathbf{X}^{f}	
Discharge from study centre			X^{g}	
Adverse event recording	Х	Х	Х	Х
Concomitant medications	Х	Х	Х	
Vital signs ^a	Х		X^h	Х
12-Lead electrocardiogram	Х		X^h	Х
Safety clinical laboratory evaluations	Х	Х	X^{i}	Х
Physical examination	Х			Х
Ophthalmology	Х			Х
Blood sample for pharmacogenetics (optional)	X ^e			
Blood sampling for total radioactivity count and AZD8931 and its metabolite (if feasible) concentration ^b			$\mathbf{X}^{\mathbf{j}}$	
Blood sampling for metabolite profiling			X^k	
Urine sampling for total radioactivity count and metabolite profiling ^c			X^l	
Faeces sampling for total radioactivity count and metabolite profiling ^{c,d}			X^m	

^a Supine blood pressure and pulse.

^b Additional collections of blood samples (5.7 mL) at 24-hour intervals may cease if no radioactivity is detected in 2 consecutive plasma samples.

^c Additional 24-hour collection of urine and/or faeces may continue until 90% total recovery is achieved or recovery in urine/faeces in the 24-hour period is less than 1% of the total administered dose of radioactivity.

Clinical Study Protocol Drug Substance AZD8931 Study Code D0102C00007 Edition Number 1.0 Date

- ^d Toilet paper (first 2 wipes) collected for the first 48 hours postdose.
- ^e Timing of sample collection at the discretion of the study centre.
- f Day 1 (0 hours).

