- ^g Day 11 (after the 240 hours postdose sample has been collected).
- ^h Predose, 24 hours postdose, and Day 11.
- ⁱ 24 hours postdose, and Day 11.
- ^j Predose, 1, 2, 4, 6, 8, 12, 24, 48, 72, 96, 120, 144, 168, 192, 216, and 240 hours postdose.
- ^k 1, 4, 6, 12, and 24 hours postdose.
- ¹ Predose (-12 to 0 hours), 0 to 6, 6 to 12, 12 to 24, 24 to 48, 48 to 72, 72 to 96, 96 to 120, 120 to 144, 144 to 168, 168 to 192, 192 to 216, and 216 to 240 hours postdose.
- ^m Predose (-48 to 0 hours), 0 to 24, 24 to 48, 48 to 72, 72 to 96, 96 to 120, 120 to 144, 144 to 168, 168 to 192, 192 to 216, and 216 to 240 hours postdose.
- ⁿ Weight only.
- ^o Drugs of abuse only.
- HIV: human immunodeficiency virus

If a subject vomits within 2 hours of dosing, the vomit should be retained for radioactivity analysis.

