5.4 Blinding and procedures for unblinding the study (Not applicable)

5.5 Treatments

5.5.1 **Identity of investigational product(s)**

The investigational product will be administered as a 2 mg/mL oral solution to achieve a 160 mg dose in an acceptable volume (80 mL). To obtain a solution of 2 mg/mL it is necessary to include citric acid monohydrate and tri-sodium citrate as buffers to control the pH to 4.5.

The 2 mg/mL radiolabeled solution contains diluted $[^{14}C]$ AZD8931 diffumerate, citric acid monohydrate, tri-sodium citrate, and water. [¹⁴C] AZD8931 difumerate (diluted with unlabelled AZD8931 difumerate to approximately 0.84 µCi/mg) is dissolved in 0.01 M citrate buffer to produce a clear, colourless oral solution. The investigational product will be provided as unit doses in Type III amber glass bottles.

Investigational product	Dosage form and stren	Manufacturer	
[¹⁴ C] AZD8931	Oral solution 160 mg AZD8931, 200	AstraZeneca	
Components	Quantity (% w/v)	Function	Standard
Diluted [¹⁴ C] AZD8931 difumerate ^a	0.2978	Active	AstraZeneca
Citric acid monohydrate	0.063	Buffer	Ph Eur, BP
Tri-sodium citrate dihydrate	0.157	Buffer	Ph Eur, BP
Water for injection	То 100	Solvent	Ph Eur

1 g of AZD8931 is equivalent to 1.489 g of AZD8931 difumerate.

5.5.2 **Doses and treatment regimens**

Each subject will receive a single oral dose of 160 mg $[^{14}C]$ AZD8931 administered on Day 1 as an oral solution. The dosing vessel will be rinsed with 2 x 50 mL water which must also be taken by the subject. This will give an effective dose equivalent of 4.7 mSv.

Water is allowed up to 1 hour predose and from 1 hour after dosing (except for water used to rinse the dosing vessel).

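### Vss/F is listed as a noncompartmental parameter after one oral dose with no intravenous reference; computed the usual way it includes absorption time and is not a steady-state volume

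*Protocol*

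**What the plan says.** Section 11.2 of the protocol lists "Volume of distribution at steady state (V_{ss}/F), for AZD8931 only" next to CL/F and Vz/F. The synopsis names the same parameter under its outcome variables, and the abbreviation list defines it. Section 11.2 fixes the approach: "Pharmacokinetic parameters will be derived using noncompartmental method", using WinNonlin or SAS.

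Section 5.5.2 gives the dosing: "Each subject will receive a single oral dose of 160 mg" of labelled drug, as an oral solution on Day 1. Section 3.1 describes a single-dose study in 6 men, and the synopsis states that there is no comparator. No intravenous dose is given, and no intravenous data are cited.

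Neither MRT nor MAT is listed as a parameter. No formula or absorption correction is given for Vss/F. CL/F and Vz/F are both called apparent, but Vss/F is not. It is also absent from the Section 11.2 list of diagnostic quantities that are listed without being summarised, so it falls under the descriptive summaries of Section 12.2.3.

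**The concern.** Noncompartmental Vss is clearance times the mean residence time of drug already in the body. That time is observed directly after an intravenous bolus. After an oral dose, the ratio AUMC/AUC also contains the average time spent being absorbed. Dividing by F deals with the fraction absorbed but not with the time that absorption takes.

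The protocol thus combines a parameter, a method and a design that do not fit together. At stake is one summarised volume. It would be too high by an amount that differs between subjects with their absorption rate, so its mean and its variability would both mix absorption with distribution. The label gives the reader no warning.

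**Working it through.** The plan states no value for Vss/F, so there is no figure to reproduce. The check is algebra, then a range under stated assumptions, then a simulation.

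**Inputs from the protocol.** One oral dose of 160 mg (Section 5.5.2); noncompartmental derivation (Section 11.2); blood sampling at "Predose, 1, 2, 4, 6, 8, 12, 24, 48, 72, 96, 120, 144, 168, 192, 216, and 240 hours postdose" (Table 1 footnotes).

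**Assumptions, not in the protocol.** Half-life 6, 12 or 24 h; first-order absorption with ka 0.3 to 2 per h; one compartment.

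**Algebra.**
- Definition: Vss = CL × MRT(iv).
- Oral data: MRT(oral) = AUMC/AUC = MRT(iv) + MAT.
- Hence CL/F × MRT(oral) = Vss/F + (CL/F) × MAT.
- Inflation factor: 1 + MAT/MRT(iv). MAT is positive, so the error is always upward.
- With one compartment, MRT(iv) = 1/ke and MAT = 1/ka, so the relative bias is ke/ka, with ke = ln 2 / half-life.

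**Numbers.** ke is 0.1155, 0.0578 and 0.0289 per h for half-lives of 6, 12 and 24 h. The relative bias ke/ka is then:

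| Half-life | ka 0.3 | ka 0.5 | ka 1 | ka 2 |
|---|---|---|---|---|
| 6 h | 38.5% | 23.1% | 11.6% | 5.8% |
| 12 h | 19.3% | 11.6% | 5.8% | 2.9% |
| 24 h | 9.6% | 5.8% | 2.9% | 1.4% |

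**Simulation.** One-compartment oral data were generated with a true volume of 100 L, the same half-lives, and ka of 0.25, 0.5, 1 and 2 per h. The noncompartmental analysis used the linear-up/log-down rule, with AUC and AUMC extrapolated to infinity.
- Dense sampling: CL/F × MRT(oral) equalled 100 × (1 + ke/ka) in every case, from 101.4 L to 146.2 L. The upper end lies above the table because ka 0.25 (MAT 4 h) is slower absorption than any column there.
- Protocol sampling times: 102.4 to 149.4 L.
- Subtracting the true MAT, which is known only in a simulation, returned 100.0 L with dense sampling and 100.6 to 104.2 L with the protocol's times.
- Vz/F = (CL/F)/λz needs no MAT. It returned 100.0 L with dense sampling and 100.3 to 106.8 L with the protocol's times.

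On either sampling scheme, most of the excess disappears once MAT is removed. What remains on the protocol's times comes from sparse sampling and also affects Vz/F.

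**The case against.** **No formula is stated.** Section 11.2 defers to standard procedures for the PK analysis, the synopsis lists parameters only where applicable, and a SAP commonly holds derivation formulas. A reader might infer that the protocol prescribes the uncorrected product. It does not; the bias follows if Vss/F is computed in the usual way. What survives is that no procedure or SAP formula can supply a disposition MRT from these data by a noncompartmental method. Fitting a compartmental model for ka would depart from the stated method. It would also have little to work on: the first postdose sample is at 1 h, by which time an assumed ka of 2 per h has absorbed 1 − e^(−2) = 86% of the absorbable dose.

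**The bias may be small.** The drug is given already dissolved, and the 39% corner needs both a short half-life and slow absorption. With ka of 1–2 per h the bias is about 1% to 12%. With 6 subjects and an assumed between-subject CV of 20–40%, the standard error of the mean is CV/√6, about 8% to 16%, so the bias would often be smaller than sampling error. This bears on severity. It does not make the parameter correct, since the bias always goes one way.

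**Vz/F is not a replacement.** A reader might infer that nothing is lost because Vz/F measures the same thing. It does so only with one compartment. With multicompartment disposition Vz exceeds Vss, and on the protocol's sampling times Vz/F was itself up to about 7% high in the simulation. This stands: Vz/F can be estimated here, but it is a different quantity.

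**Deletion is not the only cure.** A label stating that absorption time is included also removes the misreading. This stands too.

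**Conclusion.** The point holds at low severity. Vss/F as listed cannot be obtained from a single oral dose by the stated method. Computed as CL/F × oral MRT, it equals Vss/F + (CL/F) × MAT: it is biased upward and is not a steady-state volume. The direction rests on moment theory alone. The size rests wholly on assumed half-lives and absorption rates: about 1% to 39% over half-lives of 6–24 h and ka of 0.3–2 per h, and about 1% to 12% if ka is 1–2 per h.

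A reader might go further and infer that an inflated Vss/F would be carried forward as a property of the drug. The protocol does not support that. It assigns Vss/F no later use, tests no hypothesis, and bases no dose or decision rule on it. Mass balance, AUC, Cmax, CL/F, half-life and Vz/F are unaffected by this issue.

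**What to change.** Delete Vss/F from the synopsis, the abbreviation list and Section 11.2. Keep Vz/F as the reported apparent volume, without presenting it as an estimate of Vss/F.

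If a mean-time quantity is wanted, list oral MRT, or CL/F × MRT, with a label stating that it includes mean absorption time and is not to be read as Vss.

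The cost is the loss or relabelling of one listed parameter. No sample, visit or data item changes.
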